### **31.07 Lewis Cancer Self-Efficacy Scale**

**CASE: Cancer Self-efficacy Scale**

Patient Version

Instructions:

We would like to know how confident or sure you feel about some of these areas that arise when you are going through **the experience of caring for a loved one with cancer**. Please rate your degree of confidence for each sentence by circling a number from 0 to 10 using the scale shown. When you choose a higher number, you are telling us you are more confident.

Rate the confidence you feel TODAY	Not at all confident	Very confident									
1. I am confident that I can use information and resources to cope with the demands of my loved one's illness.	0	1	2	3	4	5	6	7	8	9	10
2. I am confident that I can call on my inner strengths to pull myself through my loved one's illness.	0	1	2	3	4	5	6	7	8	9	10
3. I am confident that I have what it takes to help my family through my loved one's illness.	0	1	2	3	4	5	6	7	8	9	10
4. I am confident that I can maintain close communication with my loved one about their illness.	0	1	2	3	4	5	6	7	8	9	10
5. I am confident that I can take the necessary steps to work through the demands of my loved one's illness.	0	1	2	3	4	5	6	7	8	9	10
6. I am confident that I have what it takes to help my family handle this illness.	0	1	2	3	4	5	6	7	8	9	10
7. I am confident that I can handle the challenges of my loved one's illness.	0	1	2	3	4	5	6	7	8	9	10
8. I am confident that I have ways to manage the uncertainty brought on by my loved one's illness.	0	1	2	3	4	5	6	7	8	9	10
9. I am confident that I can manage difficult interactions with my loved one's doctors, nurses, and other health care providers.	0	1	2	3	4	5	6	7	8	9	10
10. I am confident that I can put my loved one's illness into proper perspective in my life.	0	1	2	3	4	5	6	7	8	9	10

Rate the confidence you feel TODAY

Not at all

Very

	confident										confident
11. I am confident that I have the ability emotionally to help my family work through the issues caused by my loved one's illness.	0	1	2	3	4	5	6	7	8	9	10
12. I am confident that I can deal with the physical changes caused by my loved one's illness.	0	1	2	3	4	5	6	7	8	9	10
13. I am confident that I can manage what is being asked of me despite this illness.	0	1	2	3	4	5	6	7	8	9	10
14. I am confident that I have the skills to deal with the pressures the illness is causing in my close relationships.	0	1	2	3	4	5	6	7	8	9	10
15. I am confident that I have ways to manage the side effects caused by treating the cancer.	0	1	2	3	4	5	6	7	8	9	10
16. I am confident that I can keep a positive outlook in spite of the demands of this illness.	0	1	2	3	4	5	6	7	8	9	10
17. I am confident that I have ways to manage the stress associated with this illness.	0	1	2	3	4	5	6	7	8	9	10

Copyright F.M. Lewis, 1996

### 31.08 Measure of Current Status

People have different levels of various skills for responding to the challenges and demands of everyday life. The following items list several things that people are able to do--to a greater or lesser degree--to deal with daily stresses. For each item, indicate how well you currently can do what it describes. Please don't indicate what you think you should be able to do, or what you wish you could do. Be as accurate as you can in reporting your degree of confidence about being able to do each of these things. Choose from the following responses:

	I cannot do this at all	I can do this just a little bit	I can do this a medium amount	I can do this pretty well	I can do this extremely well
I am able to use muscle relaxation techniques to reduce any tension I experience	0	1	2	3	4
I become aware of any tightness in my body as soon as it develops	0	1	2	3	4
I can clearly express my needs to other people who are important to me	0	1	2	3	4
I can easily stop and re-examine my thoughts to gain a new perspective	0	1	2	3	4
It's easy for me to decide how to cope with whatever problems arise	0	1	2	3	4
I can easily recognize situations that make me feel stressed or upset	0	1	2	3	4
When problems arise I know how to cope with them	0	1	2	3	4
I notice right away whenever my body is becoming tense	0	1	2	3	4
It's easy for me to go to people in my life for help or support when I need it	0	1	2	3	4
I am able to use mental imagery to reduce any tension I experience	0	1	2	3	4
I am confident about being able to choose the best coping responses for hard situations	0	1	2	3	4
I can come up with emotionally balanced thoughts even during negative times	0	1	2	3	4
I can ask people in my life for support or assistance whenever I need it	0	1	2	3	4

### 31.09 Qualitative Exit Interview

#### INTRODUCTION

You recently took part in a study that was designed to help caregivers of with brain tumors cope most effectively with their loved ones' illness. We are now interested to know about your satisfaction with different aspects of this research study so that we continue to shape how to provide it to patients. There is no right or wrong answer. Your answers will be kept confidential and will not affect your participation in future research studies or your access to medical care.

First, I am going to ask you some questions about the timing of the sessions you had and how they were delivered.

1. This study was scheduled to start within 6 months after your loved one's diagnosis. How do you feel about the timing of the program?

- A. Right time
- B. Too early in treatment
- C. Too late in treatment

Additional Comments:

2. This study was scheduled to continue for 6 weeks. How do you feel about the length of the program?

- A. Right time
- B. Too short
- C. Too long

Additional Comments:

3. What prevented you from attending the intervention sessions? What would help you attend more of these sessions?

4. The research study was designed so that sessions can be scheduled over the phone or through telemedicine (videoconference) when in-person visits were not possible. How do you feel about the phone or video sessions?

- A. Great
- B. In-person was better
- C. Not sure

Additional Comments:

Additional Probe: Would you have preferred all sessions to be delivered over the telephone or telemedicine for convenience?

5. How do you feel about the total number of visits included in this research study (six visits total)?

- A. Right amount

Additional Comments:

B. Too few	
C. Too many	

6. How do you feel about the amount of time each session lasted?

A. Right amount	Additional Comments:
B. Too short	
C. Too long	

Now I am going to ask you some questions about the material covered in your visits.

7. During these sessions, you may have learned about strategies to help you cope most effectively with your loved ones' illness. How helpful did you find these strategies?

A. Helpful	Additional Comments:
B. Not helpful	
C. Not sure	

Additional Probe: The interviewer can remind the caregiver about specific strategies such as acceptance, mindfulness, problem-solving, self-care, communication techniques, etc. Also ask which of these strategies was the most helpful

8. Since going to the study visits, how often have you used any of these strategies on your own?

A. Daily	Additional Comments:
B. Few times/ week	
C. Once or twice	
D. Never	

9. During these sessions, you may have learned about skills or strategies that would help you gain more confidence in your ability to care for your loved one. How helpful was it to learn about these skills or strategies?

A. Helpful	Additional Comments:
B. Not helpful	

C. Not sure

Additional probe: Which of these strategies was the most helpful?

10. Since going to the study visits, how often have you used any of the skills or strategies on your own?

- A. Daily
- B. Few times/ week
- C. Once or twice
- D. Never

Additional Comments:

11. During these sessions, you may have learned about skills or strategies that would help take better care of yourself during your loved ones' illness. How helpful was it to learn about these skills or strategies?

- A. Helpful
- B. Not helpful
- C. Not sure

Additional Comments:

Additional probe: Which of these strategies was the most helpful?

12. Since going to the study visits, how often have you used any of the skills or strategies on your own?

- A. Daily
- B. Few times/ week
- C. Once or twice
- D. Never

Additional Comments:

13. During these sessions, you may have learned about skills or strategies that would help communicate more effectively with your loved one. How helpful was it to learn about these skills or strategies?

- A. Helpful
- B. Not helpful
- C. Not sure

Additional Comments:

Additional probe: Which of these strategies was the most helpful?

14. Since going to the study visits, how often have you used any of the skills or strategies on your own?

- A. Daily
- B. Few times/ week
- C. Once or twice
- D. Never

Additional Comments:

15. Is there anything else that you found helpful about this program?

16. Is there anything else that you found *not* helpful about this program?

17. What other kinds of programs focusing on improving your well-being (if any) would have been helpful *soon after* to your loved one's diagnosis?

18. What other kinds of programs focusing on improving your well-being (if any) would have been helpful *later on* following your loved one's diagnosis?

19. What other kinds of programs focusing on improving your well-being (if any) would be helpful to you now?

20. People learn information in different ways. What would you prefer in terms of how the intervention is administered?

- A. One-on-one visit with a clinician
- B. Reading information from a pamphlet
- C. Watching an informational video
- D. Telephone contact with a clinician
- F. Getting information from a mobile app

Additional Comments:

- G. Video (skype-like) sessions
- H. Group-based sessions with other caregivers

21. Is there anything else that you would like to add that we have not discussed?

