### 1.2 Specific Aims

- 1) To refine a caregiver-directed intervention and study protocol based on acceptability feedback from an open pilot study with exit interviews.

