**The goal of this proposal is to pilot a population-specific psychological intervention aimed at decreasing anxiety and promoting coping in caregivers of patients with malignant gliomas.** Our intervention is based on a conceptual framework for caregiver-directed interventions developed by our multi-disciplinary team. We recently used this framework to develop an intervention for caregivers of patients undergoing bone marrow transplantation, which was highly acceptable and beneficial to caregivers who participated in the open pilot study. While the proposed intervention is based upon this framework, we have used qualitative data collected from caregivers of patients with malignant glioma

(DF/HCC 15-500 and DF/HCC 18-171) to refine the intervention and ensure that it is targeted to the specific needs of this caregiver population. Our study population will include caregivers within the first six months of their loved one's diagnosis with malignant glioma who report clinically significant anxiety. We opted to enroll caregivers with clinically significant anxiety as they are in greatest need of a behavioral intervention focused on their distress and concerns about their loved one's health and diagnosis. Enrolled caregivers will participate in six weekly, cognitive-behavioral therapy-based, individual sessions with a mental health clinician, designed to provide them with the strategies and coping skills to manage the distress related to their loved one's illness. Findings from this project may inform the development of a future randomized efficacy trial to demonstrate the impact of the intervention on caregivers' psychological outcomes, coping, and well-being.

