#### **7.0 Study Timelines**

As this cognitive-behavioral therapy-based intervention consists of 6 weekly or biweekly sessions with a mental health clinician, an individual subject will participate for approximately 6 to 12 weeks. We anticipate that all study subjects will be enrolled within 18 months and that the study will be complete by January 2020.

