#### 9.5.9 Qualitative Exit Interview

We will use a semi-structured interview guide that will explore 1) caregiver perception of the acceptability and content of the intervention; and 2) caregiver perceptions of the benefits of receiving the intervention. Facilitators will use probes to obtain comprehensive understanding of the caregivers' perspectives. The semi-structured interview guide is detailed in [Appendix 31.09](#). The interview will last approximately 30 minutes.

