## 11.2 Analysis Plan

Feasibility will be defined by rates of enrollment and participation. We will report the proportion of eligible caregivers who agree to participate in the intervention and the proportion of intervention visits completed by each participant. Additionally, we will examine reasons for declining participation, incomplete session attendance, and early withdrawal from the study. The intervention will be deemed feasible if at least 70% (+/- 18%) of eligible caregivers are enrolled in the study and if at least 70% of enrolled participants complete  $\geq 50\%$  of the sessions. We will use descriptive statistics to summarize the demographic and clinical characteristics of caregivers enrolled in the study. We will audio-record and transcribe the individual semi-structured exit interviews and analyze qualitative data according to NIH Best Practices for Mixed Methods Research in the Health Sciences. Study staff will independently review the transcripts to create a thematic framework for interpretation. Two individuals, including the Principal Investigator, will independently code the data to enhance validity and credibility, until high reliability is achieved (Kappa>0.80). The planned sample size will allow us to collect comprehensive feedback and ensures sufficient number of participants to achieve thematic saturation. In an exploratory analysis, we will also examine changes in caregiver-reported outcomes from baseline to post-intervention using paired t-tests.

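### Exit-interview item 2 gives the program length as 6 weeks, although Section 7.0 also permits a biweekly schedule lasting up to about 12 weeks

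*Combined protocol and SAP*

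**What the plan says.** Three places in the combined protocol and SAP bear on how long the program lasts.

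- Section 2.1 gives a weekly course only: "Enrolled caregivers will participate in six weekly, cognitive-behavioral therapy-based, individual sessions with a mental health clinician".
- Section 7.0 is broader. The intervention "consists of 6 weekly or biweekly sessions with a mental health clinician, an individual subject will participate for approximately 6 to 12 weeks".
- Section 9.6 gives six 45-minute sessions and no frequency, so it does not settle the matter.

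The exit-interview guide in Appendix 31.09 follows Section 2.1. Item 2 is worded: "This study was scheduled to continue for 6 weeks. How do you feel about the length of the program". The options are right, too short and too long, with a comments field. The guide has no alternative wording for a caregiver seen every two weeks.

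The interviews serve the only specific aim (Section 1.2): "To refine a caregiver-directed intervention and study protocol based on acceptability feedback from an open pilot study with exit interviews".

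**The concern.** A caregiver on the biweekly schedule is given a duration that is not theirs and is then asked to judge the length. If that caregiver answers too long, the reply could mean that even 6 weeks is too much, or that the longer course they had was too much. Those readings lead to different refinements: fewer weeks overall, or closer spacing of the same six sessions.

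Item 2 is also the only item that asks directly about calendar length. Item 1 concerns when the program starts, item 3 barriers to attendance, item 4 phone or video delivery, item 5 the number of visits, and item 6 the length of each session. Program length is something the pilot could change, and with 25 caregivers planned there are few replies to go on.

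**Working it through.** **Inputs.** Number of sessions: 6 (Sections 2.1, 7.0 and 9.6). Interval: one week (Section 2.1), or one or two weeks (Section 7.0). Length stated to the caregiver: 6 weeks (Appendix 31.09, item 2).

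**Meaning of biweekly.** If it meant twice a week, six sessions would take 6 / 2 = 3 weeks, which lies outside Section 7.0's range. It must mean every two weeks.

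**Reproducing Section 7.0's range.** Length = sessions × interval.

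- Weekly: 6 × 1 = 6 weeks.
- Biweekly: 6 × 2 = 12 weeks.

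This returns the stated 6 to 12 weeks, so sessions × interval is evidently the protocol's way of counting.

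**Comparing the stem on the same counting.**

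| Schedule | Length (weeks) | Stem (weeks) | Difference (weeks) |
|---|---|---|---|
| Weekly | 6 | 6 | 6 − 6 = 0 |
| Biweekly | 12 | 6 | 12 − 6 = 6 |

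The stem is right for the weekly schedule and about 6 weeks short for a fully biweekly one.

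**How many caregivers.** The documents do not say how many will be seen every two weeks. With 25 planned (Section 11.1), the number affected lies between 0 and 25.

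**What the replies feed.** Feasibility in Section 11.2 rests on the enrollment rate and on session completion. Neither uses item 2. The paired t-tests use the questionnaires, not the interview.

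**The case against.** The best defense is that this is one prompt in a semi-structured guide, used by staff trained in qualitative interviewing (Section 9.7). Nothing requires verbatim delivery, and Section 9.5.9 says: "Facilitators will use probes to obtain comprehensive understanding". Caregivers know how long their own course ran, and the lead-in to this part of the interview announces "some questions about the timing of the sessions you had and how they were delivered". Items 5 and 6 help to separate a complaint about the number of visits or the minutes per session from one about calendar length, and open items 3, 16 and 21 let timing concerns surface. The analysis works from transcripts: "Study staff will independently review the transcripts to create a thematic framework for interpretation". No tabulation of the closed options is planned. Finally, item 2 agrees with Section 2.1, so it could be read as describing the nominal plan.

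Most of this stands, and it is why the point is minor. It does not remove the point. Section 7.0 presents biweekly sessions as a permitted schedule, not as slippage from a weekly plan, so 6 weeks is not the planned length for a caregiver on that schedule. Items 4, 7, 9, 11 and 13 carry a written additional probe and item 2 does not, so clarification depends on the interviewer noticing the mismatch. None of the safeguards corrects the figure.

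Two stronger readings are tempting, and the documents support neither.

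- A reader might measure from first to last session, giving 5 × 2 = 10 weeks for a biweekly course, and set that against the stem's 6, or build percentages from mixtures of one- and two-week gaps. That mixes two ways of counting: from first to last session a weekly course lasts 5 × 1 = 5 weeks, not 6. A consistent comparison is 6 against 12 or 5 against 10. Section 7.0 describes no mixture of gaps.
- A reader might infer that the acceptability findings or the feasibility verdict are biased. The mismatch lies in the wording of a question. No result is shown to be distorted, and no feasibility criterion draws on it.

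**Conclusion.** The point holds as a minor error in a data-collection instrument. Item 2 states 6 weeks where Section 7.0 allows up to about 12, so it can understate a biweekly caregiver's program by up to about 6 weeks and leave that caregiver's reply on length ambiguous. The underlying cause is the disagreement between Sections 2.1 and 7.0 on session frequency.

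This rests on three assumptions: that at least some caregivers are seen every two weeks, that interviewers use the item roughly as written, and that Section 7.0's 12 weeks refers mainly to the sessions. Section 7.0 gives that figure for participation, which may include a little time around the sessions, hence *up to about*. If no caregiver follows the biweekly schedule, the stem is correct for everyone. Weekly caregivers' answers are unaffected in any case.

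The textual mismatch is certain. Its practical consequence is small and cannot be quantified further from the documents.

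**What to change.** 1. Reword the stem of item 2 to drop the fixed figure, for example: *Your six sessions were planned weekly or every two weeks, over about [this caregiver's number of] weeks.* The question on length and its response options can stay. If filling in a number is impractical, *about 6 to 12 weeks* would do.
2. Interpret item 2 replies against each caregiver's own schedule. Section 11.2 provides for "the proportion of intervention visits completed by each participant", but neither it nor the data table in Section 11.3 mentions session dates. A note of the schedule, or of the first and last session dates, would have to be kept for each caregiver.
3. Align Section 2.1 with Section 7.0, so that the protocol gives one account of session frequency.

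A separate stem for caregivers who stop early is optional.

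The cost is one reworded sentence in the guide, one corrected sentence in the background and a small amount of data entry. No visit, questionnaire, endpoint or change in sample size is needed.

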### **31.10 Oncologist Permission to Approach Email Template**

Dear [Oncologist],

The caregiver of your patient, **[Patient Name] (MRN)**, is potentially eligible for [name] pilot study of a psychological intervention aimed at decreasing anxiety and promoting coping in caregivers of patients with malignant gliomas. Would it be alright if I approached [patient] and his/her caregiver, if present, before after his/her appointment with [provider] on **[date]** at **[time]** to introduce the study and see if they're interested in participating?

Thank you!  
[Staff Name]

### **31.11 Letter Template for At-Home Survey Completion by Mail**

Dear [Caregiver],

Thank you so much again for your interest in our study assessing the effectiveness of a psychological intervention for caregivers of loved ones with malignant gliomas. The attached questionnaires will help us determine whether or not you are eligible to participate in the study. Once you've completed them, please mail them back in the enclosed prepaid and addressed envelope. Don't hesitate to reach out if you have any questions about questionnaires or the study!

Thank you,  
[Staff Name]  
[Staff Phone]  
[Staff email]

### **31.12 Template for REDCap Survey Invitation**

Dear [Caregiver],

Thank you so much again for your interest in our study assessing the effectiveness of a psychological intervention for caregivers of loved ones with malignant gliomas. Please find below a link to some questionnaires which will help us determine whether or not you are eligible to participate in the study. Please don't hesitate to reach out if you have any questions about questionnaires or the study!

Thank you,  
[Staff Name]  
[Staff Phone]

### **31.13 Phone Script for Survey Administration**

Hello, this is [staff name] calling from Massachusetts General Hospital. How are you today?

Thank you so much for your interest in our study assessing the effectiveness of a psychological intervention for caregivers of loved ones with malignant gliomas. As I mentioned when we spoke in clinic, we have a few surveys which will help us to determine whether or not you're eligible for the study. Do you have about 10 minutes now to complete them over the phone with me?

*(If yes): Complete GAD-7 ([Appendix 31.01](#)) with caregiver and score immediately.*

*If eligible (GAD-7 score  $\geq 5$ ): Continue to Demographics Survey ([Appendix 31.03](#)) and Locator Form ([Appendix 31.04](#))*

*When complete:* Thank you so much for your time today! We will be in touch with you soon to begin scheduling your sessions with a psychologist or social worker. If you have any questions, please don't hesitate to reach out. I can be reached at [staff contact information]. I hope you have a great day!

*If ineligible (GAD-7 score  $< 5$ ):* Thank you so much for your time and interest! Unfortunately, based on your answers to this questionnaire, you are not eligible for the study at this time. However, if you'd like any more information about support for caregivers, we'd be happy to reach out to your loved one's

oncologist to have them refer you to the Brain Tumor Clinic social worker. Is this something you would be interested in?

*(If yes): Okay, I will go ahead and contact [oncologist's name] about this for you!*

*(If no): Okay! You can always talk to [oncologist's name] if you feel like this might be a helpful resource later.*

Thank you so much for your time today! We really appreciate your interest in the study and are sorry that you're not eligible at this time. Please don't hesitate to reach out if you have any questions. I can be reached at [staff contact information]. I hope you have a great day!

*(If no): When would be a more convenient time for me to call you?*

*When alternate call is scheduled: Thank you so much! I look forward to speaking with you on [date] at [time]. Have a great day!*

*Voicemail script:*

Hello, this is [name] calling from Massachusetts General Hospital. I'm reaching out to get in touch with [caregiver name] regarding a research study that he/she was interested in participating in. Please give me a call back when you have a chance. I can be reached at [staff contact information]. Thank you!

